A total of up to 40 pregnant women will be prospectively recruited into the study. As this is an 'open-label' study whose group stratification is based on subject characteristics (willingness to wear CGM, subject possession of iPhone, iPad, or iPod touch, follower possession of iPhone, iPad, or iPod touch), we cannot predict the number of subjects per treatment arm. Based on our current pregnant population's willingness to use CGM and device usage, we anticipate that 10 subjects will be in Group 1, 20 subjects in Group 2, and 10 subjects in Group 3. We will include up to 30 additional women in Group 3 identified through a retrospective chart review who were pregnant around the time of study enrollment and before the study began.

In addition, there will one main follower for each prospectively enrolled pregnant subject (up to 40 adults) who will be asked questions once per month about knowledge of the subject's glucose trends and interventions that s/he may have done on her behalf over the last month.

What is the schedule of events for the treatment groups?

After screening, when pregnancy is confirmed subjects will be stratified to Group 1, 2, or 3. Subjects in all groups will have similar study/clinic visits for data acquisition at the screening, pregnancy visits (which occur a minimum of monthly throughout gestation), and post-partum clinic visit. All subjects will be required to test blood glucoses at least 7 times a day throughout pregnancy. All subjects will be asked to log the SMBG values 7 times a day with insulin doses for meals for 1 week every trimester of the pregnancy.

Subjects stratified to CGM wear will be provided with a Dexcom G4 CGM, transmitter, and sensors (4 per month). Subjects stratified to CGM wear who want to use their personal Dexcom G5 devices will be asked to provide Dexcom mobile usernames (if they use G5 with an iPhone) and will be provided with sensors (4

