There will also be a control arm of pregnant patients at the BDC identified through a retrospective chart review who were pregnant around the time of study enrollment or before and who did not use a CGM device throughout their pregnancies. The retrospective chart review will collect data on a subject's medical history, diabetes complications, medications, vital signs, height/weight, A1C, insulin doses, glucose meter downloads, insulin pump downloads (if applicable), and CGM downloads (if applicable) for the most immediate pre-conception visit, all pregnancy visits, and the post-partum visit. Subjects identified through the retrospective chart review will not have filled out any of our questionnaires (baseline, hypoglycemic fear, and postpartum questionnaires), nor will they have had followers who filled out questionnaires. They will not be asked to fill out these questionnaires.

Inclusion Criteria:

Subjects that meet the following criteria will be considered for admission to the study:

1. Signed informed consent before any study-related activities
2. Female aged 18 years and older with T1D duration >1 year
3. Pregnancy with confirmation of gestational age 13 weeks or less
4. Willingness to routinely practice at least 3-7 blood glucose measurements per day
5. Using MDI or CSII therapy
6. Any A1C level
7. Ability and willingness to adhere to the protocol including scheduled study visits for the duration of the pregnancy
8. Able to speak, read, and write English

Exclusion Criteria:

Subjects will be excluded from the study if any of the following apply:

1. Unwilling to sign informed consent and participate in the study
2. Female age 17 years or younger
3. T1D duration <1 year
4. Pregnancy in gestational week 14 or higher
5. Extensive skin changes/diseases that inhibit wearing a sensor on normal skin
6. Severe known allergy to adhesives within the last 3 months
7. Any other condition, as determined by the investigator, which could make the subject unsuitable for the trial, impairs the subject's suitability for the trial, or impairs the validity of the informed consent

Risks and Justification of Procedures:

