All AEs, reported spontaneously by the subject, as well as those noted by the investigator or study staff, regardless of seriousness, severity or expectedness will be recorded on source documents from the time of obtaining the informed consent.

Severe hypoglycemia as defined as a hypoglycemic episode requiring assistance or hospitalization with or without an SMBG is to be reported as an SAE. A hypoglycemic event “requiring assistance” is determined when the subject is unable to treat the event on her own. Any untoward event resulting in hospitalization, extension of hospitalization, death, or threat of death will also be considered an SAE. SAEs will be reported to the DSMB. The endpoints of A1C and mean glucose readings will be excluded from SAE reporting.

Weakness of the Study

This is not a randomized clinical trial, as the Dexcom remote monitoring technology is not available for other types of handheld devices besides the iPhone, iPad, and iPod Touch. This is a pilot study as no one has previously evaluated the role of this mobile technology in diabetes care complicated by pregnancy. Our goal is to learn from this study and plan for a much larger study where handheld devices are also provided and thus randomization can occur in the future after implementing changes that will be learned from this pilot study.

Statistical Analysis Plan:

Statistical analysis is expected to be completed within 6 months of the last study visit of the last enrolled subject. Analysis will be conducted with an intention to treat approach. We will aim to recruit up to 40 pregnant subjects and plan for a 20% drop-out rate (n=8) to have 32 subjects complete the study. We aim to enroll up to 40 followers, but as their participation will be not be obligatory outcomes will not depend on their enrollment. As this is a pilot-study and has no formal power, calculations will be performed for the primary or secondary endpoints.

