The primary endpoints are glucose variability and changes detected by hypoglycemic fear survey. We will measure indices of glucose variability (mean glucose \pm SD, % of glucose within/above/below target ranges, J Index, High Blood Glucose Index [HBGI], Low Blood Glucose Index [LBGI], Mean Amplitude of Glycemic Excursions [MAGE], CONGA_n) throughout pregnancy using the SMBG 7-point profiles for one week taken once per trimester. Hypoglycemic fear survey results will be assessed once monthly over the pregnancy. We will compare outcomes within individuals over time and between individuals of the different study arms. We will test whether outcomes differ between women using Dexcom alone and women using Dexcom with Share™ using interaction terms, and will stratify analyses if differences by group are greater than 10 mg/dL in mean glucose levels are detected. Since SMBG logs will be taken at multiple time points over the pregnancy and since CGMs will be worn continuously for the duration of each pregnancy, linear mixed models will be used to assess changes in outcome measures (GV, time spent in target below or above target) over time in each trimester of pregnancy. We will use linear mixed models to assess changes in the hypoglycemic fear survey in each month of the pregnancy. Secondary endpoints include A1C differences among study arms. Improvement in glycemic variability parameters with a possible reduction of A1C by 0.3%, measured as the difference of the mean A1C laboratory values of the arms of the study between baseline (0-3 months, first trimester), second trimester (3-6 months), and third trimester (6 to 9 months). Mixed models account for missing data, allow for an unstructured covariance matrix for repeated measures, and account for inter-subjects correlation of measurements. Secondary outcomes will be used

in the same mixed models. Differences in frequency of low alert glucose rates, high alert glucose rates, and interventions for low or high glucose values among the followers for each study arm will be analyzed with student t-tests. A p-value < 0.05 will be considered significant, and we will perform statistical analyses with SAS software (version 9.3, SAS Institute, Cary NC).

Publication Strategy:

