The BDC is a leading clinical T1DM clinical and research center. All study personnel will attend an investigator's meeting, which will be organized and conducted before trial initiation. All subjects will sign an informed consent form approved by Western Institutional Review Board (WIRB) and the Colorado Multiple Institutional Review Board (COMIRB).

Study results will be presented at national and international conferences including the Scientific Sessions of the American Diabetes Association (ADA), EASD, ATTD, etc. The Principal Investigator may submit study results for publishing to peer reviewed scientific journals, particularly within the fields of diabetes and endocrinology.

Table 1: Study Procedures for Subjects

Visit	1	2	3 - 13	14
Study Week	0	1	5-40	44-52
Informed Consent and Eligibility Criteria	X			
Demographic Data, Medical History	X			
Concomitant Medications	X	X	X	X
Adverse Events	X	X	X	X
Physical Exam	X	X	X*	X
Urine Pregnancy Test		X		
A1C	X	X	X	X
Vital Signs, Height, Weight	X	X	X	X
Record Basal, Bolus, Total Insulin Dose**	X	X	X	X
SMBG Questionnaire		X	X*	X
Glucose Meter Download	X	X	X	X
Insulin Pump Download (if applicable)	X	X	X	X
Dexcom™ CGM Training and Education (if needed, Groups 1 & 2)		X		
CGM sensor insertion		X	X	
CGM Removal/ Download		X	X	X
Record interventions of a 3 rd party for a subject's high or low glucose levels		X	X	X
Hypoglycemic Fear Questionnaire		X	X*	X
BDC Pregnancy CGM Post-Partum Questionnaire				X

* Once per trimester.

[figure not shown]
** From insulin pump download or record of patient's MDI insulin use.

Table 2: Study Procedures for Followers

Visit	1	2	3 - 13	14
Study Week	0	1	5-40	44-52
Informed Consent and Eligibility Criteria	X			
Follower Questionnaire			X*	X

* Once per month.

Figure 1 Study design:

*Visit 1 will apply for women screened at a pre-conception counseling visit. Women screened in the 1st trimester may combine visits 1 and 2.

**Visits 3 through 13 for pregnancy care and study follow-up.

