Appendix C

Hypoglycemic Fear Survey

Subject ID: _____

Clinic Visit: (dd/mmm/yyyy) : _____ / _____ / _____

Visit (check one): Baseline First Trimester Second Trimester Third Trimester Post-Partum

This survey is intended to find out more about how low blood sugar makes people feel. Please answer the following questions as frankly as possible.

I. Behavior. Below is a list of things people with diabetes sometimes do in order to avoid low blood sugar. Read each item carefully. Circle one of the numbers to the right that best describes what you do during your daily routine to avoid low blood sugar.

	Never	Rarely	Sometimes	Often	Very often
1. Eat large snacks at bedtime	1	2	3	4	5
2. Avoid being alone when my sugar is likely to be low	1	2	3	4	5
3. If test urine, spill a little sugar to be on the safe side. If test blood glucose, run a little high to be on the safe side	1	2	3	4	5
4. Keep my sugar higher when I will be alone for a while	1	2	3	4	5
5. Eat something as soon as I feel the first sign of low blood sugar	1	2	3	4	5
6. Reduce my medication (insulin/pills) when I think my sugar is too low	1	2	3	4	5
7. Keep my blood sugar higher when I plan to be in a long meeting or at a party	1	2	3	4	5
8. Carry fast-acting sugar with me	1	2	3	4	5
9. Avoid a lot of exercise when I think my sugar is low	1	2	3	4	5
10. Check my sugar often when I plan to be in a long meeting or go out to a party	1	2	3	4	5

II. **Worry.** Below is a list of concerns people with diabetes sometimes have. Please read each item carefully (do not skip any). Circle one of the numbers to the right that best describes how often you worry about each item because of low blood sugar.

	Never	Rarely	Sometimes	Often	Very often
11. Not recognizing/realizing I am having a reaction	1	2	3	4	5
12. Not having food, fruit, or juice with me	1	2	3	4	5
13. Feeling dizzy or passing out in public	1	2	3	4	5
14. Having a reaction while asleep	1	2	3	4	5
15. Embarrassing myself or my friends/family in a social situation	1	2	3	4	5
16. Having a reaction while alone	1	2	3	4	5
17. Appearing stupid or drunk	1	2	3	4	5
18. Losing control	1	2	3	4	5
19. No one being around to help me during a reaction	1	2	3	4	5
20. Having a reaction while driving	1	2	3	4	5
21. Making a mistake or having an accident at work	1	2	3	4	5
22. Getting a bad evaluation at work because of something that happens when my sugar is low	1	2	3	4	5
23. Having seizures or convulsions	1	2	3	4	5

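### The plan names only an unstructured covariance and no small-sample method for the monthly fear survey; with an uncorrected F test and categorical month, about 32 women give an 11 to 17% false-positive rate

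*Combined protocol and SAP*

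**What the plan says.** The Statistical Analysis Plan makes the fear survey one of two primary endpoints. On timing it says "Hypoglycemic fear survey results will be assessed once monthly over the pregnancy", and on analysis "We will use linear mixed models to assess changes in the hypoglycemic fear survey in each month of the pregnancy". Its only statement about covariance is "Mixed models account for missing data, allow for an unstructured covariance matrix for repeated measures". It sets significance at p < 0.05 and names SAS 9.3. It does not state a denominator degrees-of-freedom method, a small-sample correction, how month enters the model, or what happens if the model fails to converge. Interaction terms are mentioned only for Dexcom alone against Dexcom with Share.

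On numbers, the same section says "plan for a 20% drop-out rate (n=8) to have 32 subjects complete the study". The section on subjects per treatment arm says "we anticipate that 10 subjects will be in Group 1, 20 subjects in Group 2, and 10 subjects in Group 3". The up to 30 chart-review controls do not add to this model. The Control Arm section says "Subjects identified through the retrospective chart review will not have filled out any of our questionnaires".

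Two other places give a different survey schedule. Table 1 lists the survey at visit 2, at visits 3-13 with the footnote "Once per trimester", and at visit 14. The form in Appendix C offers five occasions: "Visit (check one): Baseline First Trimester Second Trimester Third Trimester Post-Partum".

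**The concern.** An unstructured matrix estimates every variance and covariance separately. For three trimester values that means 6 parameters. For a monthly series it means several times as many, from about 32 women, with perhaps 8 in each of two arms. An ordinary Wald F test treats the estimated matrix as if it were known, apart from its denominator degrees of freedom. When the matrix is large relative to the number of women, that understates the uncertainty and the test rejects too often.

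At stake is a primary endpoint. A difference between arms in the course of fear scores could be called significant at two to three times the stated error rate because of the estimation method alone. The protocol's section on weaknesses says that this pilot is meant to inform a much larger study.

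**Working it through.** **The plan's own figure.** 40 × (1 − 0.20) = 32 completers, as stated. Equal dropout across arms (an assumption) turns 10/20/10 into 8/16/8.

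**Number of surveys.** The plan gives no count. Monthly visits run to week 40. Entry at week 13 gives weeks 13, 17, …, 37, which is 7 surveys. Entry at week 5 (assumed earliest) gives weeks 5, 9, …, 37, which is 9. The Table 1 and Appendix C schedule gives 3 trimester surveys, up to 5 with baseline and post-partum.

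**Variance parameters.** k(k+1)/2 for k surveys. For example, 8 × 9/2 = 36.

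**Three-arm arm-by-month test.** Month is a category and data are complete. With ν = n − 3 and q = 2(k − 1), the unstructured REML Wald F equals ν·tr(E⁻¹H)/q, where E and H are the within-arm and between-arm sums of squares and products of the month contrasts. It was simulated under no effect (100,000 draws per cell; 40,000 for k = 3) and compared with the 5% point of F(q, ν).

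**Group 1 versus Group 2 by month, within the three-arm model.** This has an exact answer. With p = k − 1, the Wald F multiplied by (ν − p + 1)/ν follows F(p, ν − p + 1). For k = 8 and 32 women: p = 7, ν = 29, and the 5% point of F(7, 29) is 2.346. Then 2.346 × 23/29 = 1.861, and P(F(7, 23) > 1.861) = 12.3%.

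| Surveys | Parameters | Three-arm, 32 women | Three-arm, 40 women | Group 1 v 2, 32 women |
|---|---|---|---|---|
| 3 | 6 | 5.7% | 5.5% | 5.5% |
| 4 | 10 | 6.4% | 6.0% | 6.3% |
| 5 | 15 | 7.5% | 6.9% | 7.4% |
| 7 | 28 | 11.0% | 9.3% | 10.3% |
| 8 | 36 | 13.6% | 10.9% | 12.3% |
| 9 | 45 | 17.0% | 13.2% | 14.8% |

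A separate simulation (8,000 draws per cell) gave 8.2% for 5 surveys in 32 women, hence the rounded range of 6 to 8% for the per-trimester schedule.

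**Other settings that the plan leaves open** (three-arm test, 8 to 9 surveys):

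- Within-subject denominator degrees of freedom, ν(k − 1), 32 women: 24 to 29%.
- Chi-square reference, 32 women: 26 to 31%.
- Small-sample-corrected F (McKeon approximation to Hotelling-Lawley), 32 women: 5.0%.
- 40 women of whom 8 drop out, within-woman correlation 0.6 assumed, 37 degrees of freedom: about 15 to 17%. With 4 to 5 surveys the same setting gave about 9 to 11%. These come from 500 simulations, with error of about 3 points.

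**The case against.** The strongest reply is that the plan does not prescribe what was tested. Four parts of it deserve an answer.

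- **Unstructured is permitted, not chosen.** The sentence lists what mixed models can do. A reader might infer that 11 to 17% is a property of the plan. The documents do not support that: with 32 women and 8 to 9 surveys, the rate runs from 5% to about 31% on the test reference alone. What remains is that no other structure is named and the only remedy, a small-sample method, is absent. Of the uncorrected references examined, n-3 is the mildest.
- **No three-arm arm-by-month test is written out, and month might be a linear term.** A linear trend would need far fewer numerator degrees of freedom, so the table does not apply to it. The interaction that is named, read as group by month with month as a category, is inflated to nearly the same degree.
- **Table 1 and the form say per trimester.** On that schedule the excess is small, about 1 to 3 points with complete data. This is fully conceded, but the analysis text itself is monthly, so the conflict has to be settled.
- **Intention to treat may bring in up to 40 women.** That lowers the rate to about 9 to 13% if all are complete, and does not help if 8 of them drop out.

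A reader might also extend the point to A1C because it is drawn monthly. That does not follow: the plan compares A1C over three trimester periods, and chart-review women supply A1C data too. Nor does the parameter count alone cause the problem, since the corrected test on the same unstructured matrix holds 5%.

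**Conclusion.** The concern holds in conditional form. The plan names one covariance structure and no small-sample method for a primary endpoint that it models monthly. If unstructured covariance is fitted to 7 to 9 surveys in 32 women with an uncorrected F on n-3 degrees of freedom, the three-arm test has a false-positive rate of about 11 to 17%. The Dexcom alone versus Dexcom with Share interaction has about 12 to 15% at 8 to 9 months. With 40 complete women the three-arm figure is about 9 to 13%, and on 3 to 5 occasions about 6 to 8%.

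These figures assume categorical month, complete data, normal errors and, for 32 women, equal dropout across arms. Non-convergence of the monthly model is a risk, not something shown here. The study is a non-randomized pilot without formal power. This is therefore a gap that should be closed, not one that invalidates the study.

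**What to change.** In the Statistical Analysis Plan:

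1. State that all mixed models use Kenward-Roger degrees of freedom. The calculation above used a different small-sample correction (McKeon) on complete data; Kenward-Roger itself was not simulated.
2. State whether month is a category or a trend, and which arm-by-month contrasts will be tested.
3. Pre-specify a fallback if the unstructured monthly model does not converge, for example a random intercept with an AR(1) or spatial-power residual over gestational week. It need not replace the unstructured matrix otherwise, because a corrected test holds its level.
4. Reconcile the monthly survey schedule in the analysis text with the per-trimester schedule in Table 1 and Appendix C. Keep Kenward-Roger on either schedule.

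Do not use an uncorrected robust (sandwich) standard error as the check. For the same three-arm test with arms of 8/16/8, complete data and 29 degrees of freedom, it rejected a true null about 65% of the time at 8 surveys and about 78% at 9 (4,000 simulations).

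The cost is a few sentences and a code option, with slightly wider intervals and larger p-values. The fallback, if used, adds reliance on a simpler correlation pattern.

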CGM data will be analyzed for mean blood glucose values, time spent in hyperglycemic (>240, >300mg/dl) and hypoglycemic (<50, <70, <80 mg/dl) ranges and various indices of glycemic variability. Laboratory analysis for A1C will be performed at baseline, monthly thereafter during the pregnancy, and post-partum. Routine blood tests will be performed in all subjects in each trimester (see Table 1).

Primary outcomes will be:

- 1) Glucose variability as measured by glucose excursions from self-monitoring blood glucose (SMBG) data through log books and downloads as well as CGM downloads and various indices [J-index, mean amplitude of glycemic excursion (MAGE), high blood glucose index (HBGI), low blood glucose index (LBGI)] from CGM downloads.
- 2) Changes detected by the hypoglycemia fear questionnaire.

Secondary outcomes will be:

- 1) How CGM alone and CGM with Share™ usage affect A1C compared to no CGM use,
- 2) Progression of diabetes complications (retinopathy, nephropathy),
- 3) Maternal and fetal outcomes (eclampsia/pre-eclampsia, live birth rates, birth weight, neonatal hypoglycemia, and other similar measures).

Introduction:

Among the US population, 29.1 million people (9.3%) have diabetes (1). Pre-existing diabetes has to be managed very carefully throughout pregnancy to optimize maternal and fetal outcomes (2). Among women

with T1DM who are pregnant, the tools that we have to regulate maternal glucose control include multiple daily injections (MDI), continuous subcutaneous insulin infusion therapy (CSII) also known as insulin pump therapy, and for high-risk individuals continuous glucose monitoring (CGM) (2). CGM use in pregnancy has been shown to be safe, to reduce the frequency of severe hypoglycemia, and to improve A1C values (3-6). Sensor-augmented pump therapy with CGM use continuously was shown to lower A1C more than intermittent use in pregnant women with T1DM (7). However, few studies have measured changes in glucose variability that occur with CGM use during pregnancy and no studies have evaluated how tools that allow family and friends (followers) to access glucose trends affect outcomes during pregnancy.

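### Two-group t-tests for three arms of follower data, and linear repeated-measures models for once-only yes/no pregnancy outcomes, do not match the data those secondary analyses will receive.

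*Combined protocol and SAP*

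**What the plan says.** **Followers.** The Statistical Analysis Plan states that differences in low-alert rates, high-alert rates, and interventions for low or high glucose "among the followers for each study arm will be analyzed with student t-tests", and that "A p-value < 0.05 will be considered significant". It names no pair of arms, overall test, rule for combining months, scoring of categories or *N/A*, or multiplicity rule. Main followers are sought in Groups 1, 2 and 3 (schedule of events for the treatment groups). They report monthly (Table 2). Each frequency item in Appendix E has five ordered categories, from *Never* to more than once daily, plus *N/A*. Follower participation is optional, and the plan says that "outcomes will not depend on their enrollment".

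**Other secondary outcomes.** For the primary glucose measures, "linear mixed models will be used to assess changes in outcome measures" over time, and the plan notes that mixed models "allow for an unstructured covariance matrix for repeated measures". It then says: "Secondary outcomes will be used" "in the same mixed models". The list of secondary outcomes at the front of the protocol includes "Maternal and fetal outcomes (eclampsia/pre-eclampsia, live birth rates, birth weight, neonatal hypoglycemia, and other similar measures". These are collected by the post-partum questionnaire, which Table 1 marks at Visit 14 only. In Appendix F the complications are yes/no questions and tick-boxes. No exact, logistic or ordinal method is named anywhere.

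**The concern.** A t-test compares two groups. Applied to three arms it must be run on several pairs, or on a pair chosen later, and the plan controls neither. The false-positive rate per outcome then exceeds the declared 0.05, and two analysts could follow the plan and reach different answers on secondary objective 1, which concerns followers' use of remote monitoring.

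A linear repeated-measures model assumes several values per woman on a scale where a straight line makes sense. A once-only yes/no outcome has neither property. The stake is the per-arm event risk. The protocol says (Weakness of the Study) that the pilot is meant to inform a much larger study, and estimated risks with impossible or zero-width intervals are poor planning inputs.

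**Working it through.** **The plan's own figure.** 40 enrolled × (1 − 0.20) = 32 completers, as stated. The anticipated prospective arms are 10/20/10. Spreading the 20% drop-out evenly (an assumption) gives 8/16/8. The documents give no event risks, category shares or within-follower correlations, so those below are assumptions.

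**(a) Follower tests**

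1. Three arms give three pairs. If the tests were independent, the chance of at least one false positive would be 1 − 0.95³ = 0.143. The pairs share arms, so simulation is needed.
2. The null simulation used category shares 35/30/20/10/5%, 3 to 9 monthly reports, within-follower correlations from 0.1 to 0.7, and both arm layouts. With one mean per follower, a single t-test rejects in 4.1–5.8% of trials. At least one of three pairs rejects in about 12–13%, with individual settings from 11% to 14%.
3. One Kruskal-Wallis test on follower means rejects in 4.0–4.9%. Kruskal-Wallis on follower medians, with pairwise tests only if it is significant, gives 3–6%.
4. If months were pooled as independent records, the per-test error would be 2 × [1 − Φ(1.96 / √(1 + (m − 1) × ICC))] for m reports. With m = 4 and ICC = 0.3 this is 0.155; with m = 9 and ICC = 0.5 it is 0.381.
5. *N/A* matters because followers in Groups 1 and 3 receive no device data. Suppose there is no true difference, but they mark *N/A* in 30%, 50% or 70% of their *Never* months. Dropping *N/A* then gives false-positive rates of about 0.05, 0.09 and 0.15. Scoring *N/A* as *Never* gives 0.04–0.05.

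**(b) Once-only yes/no outcomes**

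1. With one value per woman, the likelihood depends only on the sum of the between- and within-woman variances. For illustrative data of 1/10, 3/20 and 2/10, splits of 0/0.13, 0.05/0.08 and 0.10/0.03 give the same REML log-likelihood (14.52), and a random-intercept fit warned that the Hessian was not positive definite. The variance split is undefined; arm contrasts, which need only the sum, are not affected.
2. Worked example, 0/10, 3/20 and 1/10. SSE = 0 + 20 × 0.15 × 0.85 + 10 × 0.1 × 0.9 = 2.55 + 0.90 = 3.45, and MSE = 3.45/37 = 0.0932. The Group 1 linear 95% interval is −0.196 to 0.196; the exact interval is 0 to 0.308.
3. Full enumeration with equal risks at an assumed 5%:

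| | 10/20/10 | 8/16/8 |
|---|---|---|
| Per-arm lower limit below zero | 73–74% | 76–77% |
| No event in any arm | 0.95⁴⁰ = 12.9% | 0.95³² = 19.4% |
| Per-arm coverage, all trials | 84.4–86.4% | 78.5–80.0% |
| Per-arm coverage, at least one event | 96.9–99.2% | 97.4–99.3% |

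4. The last two rows are linked. For Group 1 at 10/20/10, 0.871 × 0.969 = 0.844. A trial with no events has zero residual variance and a zero-width interval, which counts as a miss. That accounts for the shortfall at 5% risk.
5. At 10% risk, Group 2 coverage is about 89–90% (about 92% given at least one event). At 15–30% risk, per-arm coverage is 92–96%. Between-arm difference intervals cover 94–98% at risks from 5% to 30%.
6. For a common outcome such as live birth, the mirror image applies: upper limits above 100%.
7. These layouts leave out the chart-review women, who do not complete the post-partum questionnaire. If 30 of them supplied the outcome (10/20/40), per-arm coverage at 5% risk would be 92–95%, but lower limits would still fall below zero in 74–88% of trials.

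**The case against.** **The t-test tolerates the scale.** A reader might infer that ordered, unevenly spaced categories invalidate it. With one mean per follower the error stays near 5%, so the scale alone does no harm. This part of the objection stands.

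**A two-group reading exists.** Secondary objective 1 concerns subjects wearing CGM, and the plan separately contrasts Dexcom alone with Dexcom plus Share. A t-test of Group 1 against Group 2 would hold its level. But the plan's wording covers each study arm and followers are recruited in Group 3, so the documents leave this unsettled.

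**Pooled months.** The 0.16–0.38 error rates apply only if monthly forms are treated as independent. The plan neither says so nor rules it out, and the follower is the more natural unit. Those figures show why the unit should be stated; they are not an error in the plan.

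**Coverage.** A reader might take 79–86% coverage at 5% risk to mean that the linear intervals are generally too narrow. They are not: the shortfall comes from trials with no events, where few analysts would report the interval. Nor does the plan promise model-based per-arm risks. The between-arm comparisons it does describe are acceptable.

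**Scope.** The sentence on secondary outcomes follows the A1C text, and A1C suits a linear mixed model well. Extending it to pregnancy outcomes requires the protocol's own list of secondary outcomes. That reading is fair, because no other method is given for them.

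**Conclusion.** The point holds in a limited form. The follower analysis lacks a named comparison, unit, *N/A* rule and overall test; covering all pairs raises the false-positive rate per outcome from 5% to about 12–13%. For once-only yes/no outcomes, the named model has a variance split that cannot be estimated, per-arm limits that often leave the 0–100% range, and no usable interval when there are no events.

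The documents do not support saying that t-tests are invalid on these categories, that linear intervals are too narrow in general, or that between-arm inference fails. Primary endpoints are untouched, and the study is a non-randomized pilot without formal power. The sizes rest on the assumed category shares, correlations and event risks; the mismatch between method and data does not. The change is worth making but does not threaten the study.

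**What to change.** 1. **Followers.** State that the follower is the unit. Reduce the pregnancy reports to one pre-stated summary per item, for example the mean category score, with *No* intervention scored as *Never*; keep the post-partum report separate. Compare the three arms with one overall test per outcome (ANOVA on follower means, or Kruskal-Wallis), with pairwise tests only if it is significant. Alternatively, name Group 1 against Group 2 as the single comparison. Score *N/A* as *Never* in the main analysis, report *N/A* counts by arm, and drop *N/A* only as a sensitivity analysis. Label these tests exploratory.
2. **Yes/no outcomes**, including progression of retinopathy or nephropathy summarised as ever/never. Replace the linear mixed model with counts and exact 95% intervals per arm. Use Fisher's exact test or Firth logistic regression for exploratory comparisons.
3. **Continuous outcomes.** Keep linear mixed models for A1C and other repeated measures; use ordinary linear regression for birth weight.

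**Cost.** A few lines in the Statistical Analysis Plan, with no change to forms, visits or data. Exact methods are conservative when events are few: the three-arm Fisher test has type I error of 0.005–0.009 at 5% risk and 0.03–0.05 at 15–30%. It is also unadjusted for the non-random arms. Rank tests, if chosen, cost a little power: for an assumed 0.8 SD latent shift in Group 2, 0.66–0.89 for Kruskal-Wallis on medians against 0.73–0.94 for ANOVA on means.
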